2.3 Risk/Benefit Assessment

2.3.1 Risk Assessment

The safety profile of ASP0367 is based on the results of nonclinical studies and 2 clinical studies in healthy adult participants and participants with mild or moderate hepatic impairment. Please refer to the current Investigator's Brochure for the most recent safety data.

2.3.1.1 Nonclinical

The toxicity profile of ASP0367 was similar in juvenile and adult rats, with effects targeting the heart; specifically, an increase in the incidence and/or the average grade of myocardial inflammation/necrosis in males, sometimes accompanied by an increased serum cardiac troponin I (cTnI) concentration. Myocardial inflammation/necrosis is a common, age-related background finding in male rats. The greater incidence and/or severity produced by administration of ASP0367 was not observed after dosing was stopped, suggesting the reversibility of these findings.

In juvenile rats, there were no ASP0367-related effects on the development of organ systems that undergo postnatal development, such as the nervous, skeletal and reproductive systems. No microscopic kidney findings similar to those seen in the euthanized cynomolgus monkey (in the 13-week study) were observed in any animals (rats or monkeys) up to 13 weeks of daily dosing, and renal function safety markers were normal in all other animals.

Nonclinical studies have identified the target organs of toxicity as the heart and skeletal muscle. In this phase 2 study in participants with PMM, cardiac (including cTnI, cardiac troponin T [cTnT] and creatine kinase [CK] isoenzymes found in heart muscle [CK-MB]) and skeletal muscle (including total CK and CK isoenzymes found in skeletal and heart muscle [CK-MM]) biomarkers indicative of damage will be measured frequently.

The risk of carcinogenicity has not yet been fully evaluated. Histopathological examination from the carcinogenicity study in rats has been completed and another carcinogenicity study in mice is planned. During the longer-term toxicology studies in adult Wistar Han rats (up to 26-weeks and doses up to 50 mg/kg per day) and in cynomolgus monkeys (up to 52-weeks and doses up to 500 mg/kg per day) no development of tumors was observed. However, in the 26-week rat study a dose-dependent increase in the incidence of hyperplasia of the limiting ridge of the non-glandular stomach and the incidence of hypertrophy/hyperplasia of the follicular cells in the thyroid gland were observed. In the monkey toxicology study, no proliferative lesions were observed during the course of this 52-week study.

In the 2-year carcinogenicity study, Wistar Han (RccHan®: WIST) rats were treated with ASP0367 at dose levels of 0 (water), 0 (vehicle), 10, 25 and 50 mg/kg/day for 105 weeks. The histopathological data from this 2-year study comprised neoplastic observations, revealing statistically significant increases in benign vaginal polyps and benign endometrial stromal polyps, and statistically non-significant occurrences of endometrial adenocarcinoma.

- Benign vaginal polyps were observed in the water control and 50 mg/kg/day groups. The increased incidence of benign vaginal polyps in the 50 mg/kg/day group was statistically significant compared to the water and vehicle control groups.
- Benign endometrial stromal polyps were observed at all dose levels, including the water and vehicle controls. The increased incidence of benign endometrial stromal polyps in the 25 and 50 mg/kg/day groups differed in statistical significance depending on the analysis. Of note, the overall rate of benign endometrial stromal polyps was within the range of historical control groups at the study sites for the 25 mg/kg/day group and slightly higher than historical control groups for the 50 mg/kg/day group.
- Endometrial adenocarcinomas were observed at all dose levels, including water and vehicle controls. There were no statistically significant differences between ASP0367 dose groups and the water or vehicle control groups.
- No neoplastic findings were observed in the stomach or thyroid gland.

There have been no reports of tumors in the female reproductive tract in the clinical study program to date. The safety margins for exposure at the dose levels administered to humans up to 75 mg/day compared to the exposure at the doses administered to rats are considered to be adequate in the ongoing Study 0367-CL-1201. Given the risk of carcinogenicity associated with the use of PPAR agonists and the neoplastic observations from the draft report for the 2-year carcinogenicity rat study, administration of ASP0367 is currently limited to no longer than 6 months.

In nonclinical safety pharmacology studies, ASP0367 revealed no effects on central nervous system or respiratory system function in rats at doses up to 300 mg/kg. Although ASP0367 inhibited the hERG channel current in hERG transfected HEK293 cells, no QT prolongation or other effect on the cardiovascular system was discernable in cynomolgus monkeys at doses up to 1000 mg/kg. There was no evidence of genotoxic potential with ASP0367 based on the findings from a standard battery of genotoxicity assays. ASP0367 showed no phototoxic potential in an in vitro phototoxicity study in cultured Balb/c 3T3 cells.

ASP0367 is considered unlikely to affect fertility in humans as daily oral administration of ASP0367 to rats did not affect fertility in either sex. Studies in pregnant rats and rabbits dosed during the period of major organogenesis suggest that ASP0367 is not teratogenic but may have the potential to affect fetal growth and/or survival in humans. Any potential embryofetal risks will be mitigated by enrolling participants under instruction of intensive control of pregnancy risk over the study duration.

2.3.1.2 Clinical

ASP0367 has been assessed in 4 completed phase 1 clinical studies (0367-CL-0001, 0367-CL-1102, 0367-CL-1103 and 0367-CL-1111). ASP0367 was well tolerated in the healthy adult participants and participants with mild or moderate hepatic and severe renal impairment. There were no deaths and no serious adverse events (SAEs) reported. Also, there were no discontinuations due to treatment-emergent adverse events (TEAEs). All adverse events (AEs) were transient and mild or moderate in severity. No drug-related cardiac or skeletal muscle AEs were reported. In the first-in-human Study 0367-CL-0001, one participant at the single dose of 60 mg had cTnI values above the upper limit of normal (ULN; 0.056 ng/ml and 0.047 ng/mL above the ULN of 0.045 ng/mL) at the end of study visit (8 days after a single dose) and repeat assessment poststudy on day 21, respectively, with no clinical signs associated and deemed not clinically relevant. There was no test article-related elevation in serum cTnT; CK-MB stayed within the normal range, and no participants were observed with ischemic changes or prolonged QT. Amylase and lipase elevations above the laboratory reference range were observed for a number of participants following administration of ASP0367 or placebo. There were no trends for treatment or dose, or day of onset-related trends in the frequency or magnitude of these elevations. The participants with amylase or lipase elevations remained asymptomatic and the elevations resolved without treatment. None of the amylase or lipase elevations were reported as TEAEs. There were no other clinically significant findings in laboratory tests (specifically in skeletal and other cardiac muscle markers [cTnT, CK-MB]), vital signs or electrocardiograms (ECGs; changes related to ischemia or QT interval changes).

In Studies 0367-CL-1102 (mild and moderate hepatic impaired participants and healthy matched participants) and 0367-CL-1111 (severe renal impaired participants and healthy matched participants), the incidence of TEAEs reported during study conduct was low. In each study, 2 TEAEs were reported that were considered by the investigator to be mild and related to study intervention. In the hepatic impairment study, 1 participant with mild hepatic impairment experienced nausea and 1 participant with mild hepatic impairment experienced fatigue. In the renal impairment study, 1 participant with severe renal impairment had a TEAE of troponin I increased (single episode with onset on day 2; value of 0.09 ng/mL [normal range: not reported to 0.015 ng/mL]) and 1 participant with severe renal impairment had a TEAE of lipase increased (values above ULN of 92 U/L on day 5, 142 U/L at EOS visit and 85 U/L during a follow-up unscheduled visit [normal range: 11 to 82 U/L]). None of the participants in either study required concomitant medications for the treatment of these TEAEs. There were no other clinical laboratory (hematology, biochemistry and urinalysis) results, vital signs measurements or routine 12-lead ECG measurements reported as TEAEs during the conduct of these studies. None of the participants had potentially clinically significant values or increases in liver enzymes or TBL after study intervention administration.

In the AME study 0367-CL-1103, 1 participant experienced a TEAE (diarrhea) that was considered by the investigator to be possibly related to study intervention. There were no clinical laboratory (hematology, biochemistry and urinalysis) results, vital sign measurements or routine 12-lead ECG measurements reported as TEAEs during the conduct of this study. No participant had potentially clinically significant increases in liver enzymes or TBL after study intervention administration.

ASP0367 has also been assessed in 1 completed phase 1b clinical study (0367-CL-0102) in late ambulatory and early non-ambulant patients with DMD. No SAEs, drug-related TEAEs, TEAEs leading to death or TEAEs leading to withdrawal of treatment were observed in the

12-week DB or OLE parts of the study. Similar TEAE frequencies were reported across the ASP0367 and placebo treatment groups in the 12-week DB part. These events were consistent with the underlying disease of DMD. Overall, the mean changes in clinical laboratory values and vital signs were similar between treatment groups. No significant safety issues were observed in subjects who received ASP0367.

2.3.1.3 Cardiac and Skeletal Muscle

Based on the nonclinical findings observed with ASP0367, toxicity of the heart and skeletal muscle have been identified as important potential risks, although they have been observed only in rats but not in monkeys.

Baseline cTnI values in patients with PMM are not well established. Since mitochondrial oxidative phosphorylation is the main source of energy in the heart, responsible over 95% of adenosine triphosphate synthesis [Zdończyk et al, 2020], cardiac involvement in mitochondrial diseases is common with an estimated prevalence of more than 20% in adult mitochondrial disease patients [Limongelli et al, 2010]. A single cTnI level at a fixed time point in patients with PMM is insufficient to determine clinical significance, particularly with biological variability (diurnal variation) and bioanalytic (assay variation) variability.

In addition to routine standard monitoring of safety in the proposed study (0367-CL-1201), the sponsor proposes the following screening activities and repeated sequential monitoring to address the cardiac and skeletal muscle toxicity monitoring:

All participants will undergo screening including cardiac biomarkers and ECG prior to enrollment in the study. This study appropriately excludes PMM patients with clinically significant and unstable cardiovascular disease as described in Exclusion Criteria #12 through 14. As such, the investigator will clinically correlate the cTnI level to assess eligibility. Only participants with a cTnI level below upper limit and a mean QT interval using Fridericia's correction (QTcF) of \leq 450 msec for male participants and \leq 480 msec for female participants will be allowed into the study.

Sequential cardiac muscle monitoring will include assessment of serum cardiac enzymes, including cTnI, cTnT, CK-MB and ECGs at protocol-specified intervals. Participants who experience any signs or symptoms potentially reflecting cardiac involvement will undergo ECG, echocardiogram, and have a cTnI drawn for further evaluation prior to continuing study drug. Participants who develop an increase in cardiac enzymes levels (i.e., increased cTnI) will interrupt investigational product (IP) and will undergo more intensive assessments of cardiac function such as ECG and echocardiogram for further evaluation.

Sequential monitoring for skeletal muscle injury will include assessment of CK, transaminases and lactate dehydrogenase at protocol-specific intervals. An individual participant may be required to discontinue treatment if they develop an elevation in CK levels \geq 5 times the value of the ULN or the individual's baseline value, whichever is higher and it is judged that this elevation is not related to an explainable increase including excessive movement, fall or disease state.

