6.5 Dose Modification

Dose modification for individual participants is not allowed.

Dosing may be interrupted if further evaluation is required for ongoing AE(s), clinical laboratory abnormality or intercurrent illness. The investigator will assess the resolution of the event and determine, in consultation with the medical monitor, whether resuming dosing or continued participation in the clinical study is in the best interest of the participant.

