7.2.4 Electrocardiogram

- A standard 12-lead ECG will be conducted as outlined in the schedule of assessments [Table 1] using both a central ECG reading laboratory and local ECG reading. ECGs at weeks 2 and 8 will be performed at the participant's home by a qualified healthcare provider from the home healthcare vendor. In case the home healthcare visit is not feasible, the visit can be conducted at the study site.
- ECGs will be recorded in triplicate (3 separate ECGs, 5 minutes resting prior to first ECG and at least 1 minute apart per time point), prior to blood draw and transmitted electronically for central reading. The mean of the triplicate ECG from central and local read should be used for treatment decisions and AE reporting.
- If the mean triplicate QTcF is > 500 msec at any time point, one follow-up triplicate ECG may be performed on the same day. If the follow-up mean QTcF is \leq 500 msec, the participant may proceed with IP. If the follow-up mean QTcF > 500 msec is confirmed, then the participant must discontinue IP.
- An ECG will also be performed within 24 hours of any of these events: an elevation of cTnI above the ULN (see Appendix 10.9 for reference range), or when there is an elevation of cTnT above the ULN (see Appendix 10.9 for reference range) or above the participant's baseline value if it was elevated, or when a participant has any signs or symptoms reflecting cardiac involvement, inclusive of new onset shortness of breath. If the ECG is within normal limits, a repeat of the abnormal troponin value (cTnI or cTnT) should be obtained. For any of the situations above, it may be required to interrupt or discontinue further administration of IP as described in [Section 8.1 Discontinuation of Individual Participant(s) from Study Treatment]. Participants with persistent cTnI or

cTnT elevations, abnormal ECG or abnormal echocardiogram should undergo cardiology follow up.

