8.1 Discontinuation of Individual Participant(s) from Study Treatment

A discontinuation from treatment is defined as a participant who enrolled in the study and for whom study treatment is permanently discontinued for any reason.

The participant is free to withdraw from the study treatment and/or study for any reason and at any time without giving reason for doing so and without penalty or prejudice. The investigator is also free to discontinue the participant from study treatment or to terminate a participant's involvement in the study at any time if the participant's clinical condition warrants it.

The reason for discontinuation from study treatment must be documented in the participant's medical records.

A participant must discontinue study treatment for any of the following reasons:

- Participant requests to stop treatment.
- Any clinical AE, laboratory abnormality or intercurrent illness, in the opinion of the investigator, indicates continued treatment is not in the best interest of the participant.
- Participant remains non-compliant with the protocol based on investigator's or sponsor's assessment.
- Female participant becomes pregnant.

An individual participant may be required to discontinue further administration of IP if any of the following occurs, which is considered to be clinically significant and to be considered related to IP:

- SUSAR
- Participant has a mean QTcF > 500 msec measured by a triplicate ECG. If the mean QTcF exceeds 500 msec, a follow-up triplicate ECG may be performed on the same day. If the follow-up mean QTcF is still > 500 msec, the participant must discontinue IP.
- Participant who experiences a cTnI elevation (i.e., > ULN [see Appendix 10.9 for reference range]) or a cTnT elevation above the ULN (see Appendix 10.9 for reference range) or above the participant's baseline value if it was elevated should undergo ECG and echocardiogram within 24 hours. The investigator should determine whether it is appropriate to continue administration of IP to the participant while the evaluations are being completed. If the ECG and echocardiogram are within normal limits, a repeat of the abnormal value (cTnI or cTnT) should be obtained. Participants with persistent cTnI or cTnT elevations, abnormal ECG or echocardiogram should interrupt IP and undergo cardiology follow up.

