- Participant who develops any signs or symptoms potentially reflecting cardiac involvement, inclusive of new onset shortness of breath, should interrupt IP and undergo ECG, echocardiogram, and have a cTnI drawn to be evaluated prior to continuing IP.
- Participant who develops an elevation in CK levels ≥ 5 times the value of the ULN or the individual's baseline value, whichever is higher and it has been judged that this elevation is not related to an explainable cause such as excessive activity or disease state.
- Participant who develops elevated levels of ALT or AST > 3 × ULN, or TBL > 2 × ULN persisting after 72 hours in the absence of elevated CK levels must discontinue IP. Generally, liver chemistry will be followed by repeated measurements until they return to baseline or stable values.
- Participant who presents evidence of suicidality during the C-SSRS assessments by meeting the criteria at a level of 4 or 5 since last visit must discontinue IP and upon immediate evaluation, the investigator will decide an appropriate referral.
- Participant who develops symptomatic viral infection should be evaluated by the Investigator and assessed for the need to stop IP until clinically improved.
- Participant who newly develops signs or symptoms of bulbar weakness, such as dysphagia, dysphonia, hoarseness or drooling/sialorrhea, should discontinue IP.
- Participant with a new requirement for oxygen therapy or for ventilatory support, inclusive of any respiratory device to support breathing, such as home ventilators and any form of non-invasive positive pressure ventilation (including CPAP, BiPAP, and AVAPS), should discontinue IP.

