Severe	$> 3 \times ULN$	and†	$> 2 \times ULN$

ALT: alanine aminotransferase; AST: aspartate aminotransferase; TBL: total bilirubin; ULN: upper limit of normal

†Samples taken simultaneously or within maximum 24 hours.

In addition, the participant should be considered to have severe hepatic abnormalities for any of the following:

- ALT or AST $> 8 \times ULN$
- ALT or AST > $5 \times$ ULN for more than 2 weeks

- ALT or AST > 3 × ULN and† international normalized ratio (INR) > 1.5 (If INR testing is applicable/evaluated)
- ALT or $AST > 3 \times ULN$ with the appearance of fatigue, nausea, vomiting, right upper quadrant pain or tenderness, fever, rash and/or eosinophilia (> 5%)

†Samples taken simultaneously or within a maximum of 24 hours.

The investigator may determine that abnormal liver chemistry results, other than as described above, may qualify as moderate or severe abnormalities and require additional monitoring and follow-up.

Follow-up Procedures

Confirmed moderate and severe abnormalities in hepatic functions should be thoroughly characterized by obtaining appropriate expert consultations, detailed pertinent history, physical examination and clinical laboratory tests. The study site personnel are to complete the liver abnormality case report form (LA-CRF). Participants with confirmed abnormal liver function testing should be followed as described below.

Confirmed moderately abnormal liver function tests should be repeated 2 to 3 times weekly, and then weekly or less if abnormalities stabilize or the IP has been discontinued and the participant is asymptomatic.

Severe hepatic liver function abnormalities as defined above, in the absence of another etiology, may be considered an important medical event and may be reported as a SAE. The sponsor should be contacted and informed of all participants for whom severe hepatic liver function abnormalities possibly attributable to IP are observed.

To further assess abnormal hepatic laboratory findings, the investigator is expected to:

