- Obtain a more detailed history of symptoms and prior or concurrent diseases. Symptoms and new-onset diseases are to be recorded as "AEs" within the CRF. Illnesses and conditions such as hypotensive events and decompensated cardiac disease that may lead to secondary liver abnormalities should be noted. Nonalcoholic steatohepatitis is seen in obese hyperlipoproteinemic and/or diabetic participants and may be associated with fluctuating AT levels. The investigator should ensure that the medical history form captures any illness that predates study enrollment that may be relevant in assessing hepatic function.
- Obtain a history of concomitant drug use (including nonprescription medication, complementary and alternative medications), alcohol use, recreational drug use and special diets. Medications are to be entered in the CRF. Information on alcohol, other substance use and diet should be entered on the LA-CRF or an appropriate document.
- Obtain a history of exposure to environmental chemical agents.
- Based on the participant's history, other testing may be appropriate including:
 - Acute viral hepatitis (A, B, C, D, E or other infectious agents)
 - Ultrasound or other imaging to assess biliary tract disease
 - o Other clinical laboratory tests, including INR and direct bilirubin
- Consider gastroenterology or hepatology consultations.
- Submit results for any additional testing and possible etiology on the LA-CRF or an appropriate document.

Study Treatment Discontinuation

In the absence of an explanation for increased liver chemistry tests, such as viral hepatitis, preexisting or acute liver disease, or exposure to other agents associated with liver injury, the participant may be discontinued from study treatment. The investigator may determine that it is not in the participant's best interest to continue study treatment. Discontinuation of study treatment should be considered if the participant has severe hepatic abnormalities.

In addition, if close monitoring for a participant with moderate or severe hepatic laboratory tests is not possible, study treatment should be discontinued.

Hy's Law definition: Drug-induced jaundice caused by hepatocellular injury, without a significant obstructive component, has a high rate of bad outcomes, from 10% to 50% mortality (or transplant).

The 2 "requirements" for Hy's Law are:

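### Protocol version 9.0 gives conflicting study-drug instructions for a raised cTnI and for a persistent liver-test elevation without raised CK

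*Protocol*

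**What the plan says.** **Raised cTnI.** The risk section, Protocol 2.3.1.3, says: "Participants who develop an increase in cardiac enzymes levels (i.e., increased cTnI) will interrupt investigational product (IP", followed by ECG and echocardiogram. It gives no numerical threshold and no role for investigator judgement.

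Section 8.1 sets the trigger at cTnI above ULN and asks for ECG and echocardiogram within 24 hours. On dosing in the meantime it says: "The investigator should determine whether it is appropriate to continue administration of IP to the participant while the evaluations are being completed". Interruption comes later and under conditions: "Participants with persistent cTnI or cTnT elevations, abnormal ECG or echocardiogram should interrupt IP and undergo cardiology follow up".

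Sections 7.2.4 and 7.2.5 say that "it may be required to interrupt or discontinue further administration of IP as described in [Section 8.1", so they hand the question to 8.1. Section 6.5 gives a general permission: "Dosing may be interrupted if further evaluation is required for ongoing AE(s), clinical laboratory abnormality or intercurrent illness".

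**Raised liver tests.** Section 8.1 says that a participant with ALT or AST above 3 × ULN, or total bilirubin above 2 × ULN, "persisting after 72 hours in the absence of elevated CK levels must discontinue IP".

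Appendix 4 (Section 10.4, Table 9) labels either of those elevations alone as moderate. Its follow-up text reads: "Confirmed moderately abnormal liver function tests should be repeated 2 to 3 times weekly, and then weekly or less if abnormalities stabilize". The same sentence goes on to give IP already stopped, in a participant without symptoms, as another ground for less frequent testing. Where no explanation is found, the "participant may be discontinued from study treatment". For severe abnormalities, Appendix 4 asks only that discontinuation be considered.

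**The concern.** The protocol names heart toxicity as an important potential risk (2.3.1.3), and its benefit-risk conclusion (2.3.3) relies on precautions such as cardiac monitoring. A site following 2.3.1.3 interrupts study drug at any cTnI increase. A site following 8.1 may keep dosing through the work-up.

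For a persistent liver elevation without raised CK, a site following 8.1 stops the drug permanently, while a site following Appendix 4 may continue with repeat tests. Participants with the same results could be managed differently, and a deviation could not be judged consistently.

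There is a smaller statistical consequence. Treatment discontinuation is an intercurrent event under a hypothetical strategy, and 6MWT data more than 7 days after the last dose are ignored. Uneven stopping would change which data enter the primary analysis. This runs mainly through the liver rule, because the cTnI conflict concerns interruption, which is not a listed intercurrent event.

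**Working it through.** No plan figure has to be reproduced. The check sets the current version 9.0 passages side by side; nothing rests on the summary of changes.

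**1. First cTnI above ULN, work-up not yet complete**

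| Source | Study-drug action |
|---|---|
| 2.3.1.3 | Interrupted, stated as certain |
| 8.1, during work-up | Investigator decides |
| 8.1, after work-up | Interrupt if elevation persists or ECG/echocardiogram abnormal |
| 7.2.4, 7.2.5 | Interruption or discontinuation possible; refer to 8.1 |
| 6.5 | General permission to interrupt |

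If the investigator elects to continue, 8.1 is satisfied and 2.3.1.3 is not. If the repeat value is normal and both cardiac tests are normal, 8.1 never calls for interruption, yet 2.3.1.3 would already have required it. The conflict is between 2.3.1.3 and 8.1; the other three sections are context.

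**2. Liver elevation persisting after 72 hours, CK not raised, no other explanation found**

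| Source | Study-drug action |
|---|---|
| 8.1 | Mandatory discontinuation |
| Appendix 4, moderate (either threshold alone) | Retest 2 to 3 times weekly; stopping is optional |
| Appendix 4, severe (both thresholds, or the further listed criteria) | Discontinuation to be considered |

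The thresholds are identical. The order of strictness is also inverted: 8.1 requires stopping at a level Appendix 4 calls moderate, while Appendix 4 requires only consideration at the severe level. The overlap is limited to persistent elevations without raised CK; the optional-stopping clause further requires that no other explanation was found. Outside that overlap the two texts do not clash.

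**3. Lead-in to the 8.1 list.** It says a participant may have to discontinue if an event is clinically significant and related to IP, yet the QTcF, liver and C-SSRS bullets beneath it are mandatory. This is a lesser drafting point. The specific QTcF sentences in 7.2.4 and 8.1 agree with each other.

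**4. How often a decision could arise.** Table 10 lists cTnI, ALT, AST, total bilirubin and CK in both the full and the abbreviated biochemistry panels. From Table 1:

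- full panel after baseline: weeks 4, 12, 24, 28 = 4
- abbreviated panel: weeks 1, 2, 3, 8, 16, 20 = 6
- total after baseline: 4 + 6 = 10
- before the week 24 end-of-treatment visit: 10 − 2 (weeks 24 and 28) = 8

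Table 7 agrees: 5 full draws including week 0, so 4 after baseline, plus 1 at week 2 and 5 at the other phone-call visits, giving 10. These counts describe opportunities for a trigger, not participants affected.

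**The case against.** The strongest argument is that the version 9.0 text may never have governed a treatment decision. The SAP places all participants under version 7.0 or earlier, reports the recommendation to stop for futility (6.7.1), and records analyses removed because of that stop (Section 7 of the double-blind SAP). This stands, and it limits the consequence to any dosing under this text or its reuse.

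Second, 2.3.1.3 is risk narrative, while 7.2.4 and 7.2.5 direct the site to 8.1, so 8.1 looks operative. That is a reasonable inference, but the protocol states no order of precedence, and 2.3.1.3 describes the monitoring offered as mitigation for a named risk. It is fair that 6.5, 7.2.4 and 7.2.5 do not themselves contradict 8.1.

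Third, Appendix 4 is monitoring guidance for a wider group, including raised-CK and explained cases, and provides for participants already off drug. It also firmly calls for discontinuation where close monitoring is not possible. The texts can be read in sequence: retest within 72 hours, then act under 8.1 on what persists. But neither the 8.1 liver bullet nor the Appendix 4 discontinuation text refers to the other. The retest schedule also treats stopped IP as only one possible circumstance, so it contemplates people still dosing.

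Fourth, the 8.1 lead-in might restrict the liver bullet to clinically significant, drug-related events and so bring it closer to Appendix 4. Even then, stopping would be mandatory in one place and optional in the other for those events.

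**Conclusion.** The concern holds as stated. Two triggers carry conflicting current instructions: increased cTnI (2.3.1.3 against 8.1), and ALT or AST above 3 × ULN or bilirubin above 2 × ULN persisting after 72 hours without raised CK (8.1 against Appendix 4). The analytes are scheduled at 10 post-baseline visits, 8 of them before the end-of-treatment visit.

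The documents give no expected rate of either trigger in this population, so neither the number of participants affected nor any effect on the treatment-discontinuation intercurrent event can be sized. Realised impact on this trial may be nil. The point should still be fixed, because conflicting instructions on a named cardiac risk and on liver injury are an error in the text and not merely missing detail. Confidence is high, since the finding rests on wording alone. It takes no position on which rule is clinically right.

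**What to change.** Reconcile 2.3.1.3 with 8.1 on cTnI, including the trigger each uses, and check that 6.5, 7.2.4 and 7.2.5 follow the result. Reconcile 8.1 with Appendix 4 on liver tests, stating how the 8.1 rule relates to the moderate and severe categories and to raised CK, and add cross-references in both directions. Bring the 8.1 lead-in into line with its mandatory bullets and with 7.2.4. The sponsor's medical team should decide which rule applies in each case.

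The cost is protocol wording or a clarification letter, with no new procedures or data. If dosing under version 9.0 will not occur, the correction should be made before the text is reused in another protocol.
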